### **10.4 Data Analysis**

Descriptive statistics, including mean, median, standard deviations and ranges for all continuous measures will be tabulated and reported. Percentages and frequencies for all categorical measures will also be presented. Time to events endpoints will be reported using Kaplan-Meier estimates, with 95% confidence intervals (CIs) for median time to event.

#### **10.4.1 Demographics and Baseline Characteristics**

Demographic and baseline disease characteristics will be summarized in order to assess the comparability of the treatment groups descriptively. Data to be tabulated will include demographic features such as age, sex and race, as well as disease-specific characteristics.

The number and percentages of patients screened, randomized, treated, completed the treatment/study and withdrawn from treatment/study for any reasons will be presented overall and also by dose level.

#### **10.4.2 Efficacy Analysis**

All efficacy analyses will be performed using the EFF.

Measurement of PSA levels, bone scans and CT/MRI scans will be performed for all patients at screening, during the study, and at follow-up visits before a subsequent anti-cancer therapy or death.

- PSA response rate, PSA confirmed response is defined as the proportion of participants with a reduction in the PSA level of  $\geq 50\%$  from baseline to the lowest post-baseline PSA results, measured twice, at least 3 weeks apart by the PCWG3 criteria.

*CONFIDENTIAL*

Study Drug: AC176

Sponsor/Development Innovations Study Number: AC176-001/GU 207

Final Protocol: 10 July 2023 Version 4.0

- Objective Response Rate (ORR), defined as the proportion of patients with confirmed complete response (CR) or partial response (PR) (i.e., 2 CRs or PRs at least 4 weeks apart) according to the PCWG3-modified RECIST Version 1.1 criteria (see [Appendix B](#)).
- Duration of Response (DoR), defined as the time from the date of first documented response (the first CR or PR which has been subsequently confirmed) until date of documented progression or death in the absence of disease progression.
- Time-to-Progression (TTP) based on PCWG3-modified RECIST v1.1 and/or PCWG3 PSA criteria ( $\geq 25\%$  increase and  $\geq 2$  ng/mL increase above the nadir or baseline value for patients who had a PSA decrease on treatment, which is confirmed by a second value 3 or more weeks later. For patients without a decrease on treatment, PSA progression is defined as  $\geq 25\%$  increase and an absolute increase of  $\geq 2$  ng/mL after 12 weeks.), defined as the time from start of study treatment to disease progression.
- Radiographic Progression-Free Survival (rPFS), based on PCWG3-modified RECIST v1.1 criteria. rPFS is defined as the time from the first study drug administration to first objective evidence of radiographic disease progression assessed by the Study Investigator, or death, whichever occurs first.
- Progression-free Survival (PFS), based on PCWG3-modified RECIST v1.1 and/or PCWG3 PSA criteria. PFS is defined as the time from first study drug administration until objective disease progression (based on bone or CT/MRI scans), or PSA, or death, whichever occurs first.

For ORR, patients without a post-baseline tumor assessment will be classed as not evaluable (NE) and considered as non-responders, and estimates and the associated 95% CIs (based on the Clopper-Pearson method) in each dose level will be calculated.

For TTP, Kaplan-Meier curves will be generated and the median time to event, and the associated 95% CIs will be provided.

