## **2. STUDY OBJECTIVES AND ENDPOINTS**

**Table 3 Study Objectives and Corresponding Endpoints**

Objectives:	Endpoint/Variable:
Primary Objective: Evaluate the safety and tolerability of AC176	Dose-limiting toxicities (DLTs) Adverse events (AEs)/Serious adverse events (SAEs) Vital signs Clinical chemistry/hematology parameters Electrocardiograms (ECGs)
Secondary Objectives: Characterize the pharmacokinetics (PK) profile of a single dose and after multiple doses of AC176  Evaluate the preliminary anti-tumor activity of AC176 on prostate-specific antigen (PSA) response rate	Endpoint/Variable: PK parameters  PSA confirmed response is defined as the proportion of participants with a reduction in the level of PSA of $\geq 50\%$ from baseline to the lowest post-baseline PSA results, measured twice, at least 3 weeks apart, by the Prostate Cancer Working Group 3 criteria (PCWG3, Scher et al. 2016 )

Objectives:	Endpoint/Variable:
Evaluate the preliminary anti-tumor activity of AC176 on objective response rate (ORR) for patients with measurable disease	ORR based on PCWG3-modified Response Evaluation Criteria in Solid Tumors (RECIST) v1.1 ( Eisenhauer et al. 2009 )
Evaluate the preliminary anti-tumor activity of AC176 on duration of response (DoR)	Duration of Response (DoR) is defined as the time from the date of first documented response until date of documented progression or death in the absence of disease progression
Evaluate the preliminary anti-tumor activity of AC176 on time-to-progression (TTP)	TTT based on PCWG3-modified RECIST v1.1 and/or PCWG3 PSA criteria ( $\geq 25\%$ increase and $\geq 2$ ng/mL increase above the nadir or baseline value for patients who had a PSA decrease on treatment, which is confirmed by a second value 3 or more weeks later. For patients without a decrease on treatment, PSA progression is defined as $\geq 25\%$ increase and an absolute increase of $\geq 2$ ng/mL after 12 weeks.)
Evaluate the effect of AC176 on radiographic progression-free survival (rPFS)	Radiographic disease progression based on PCWG3-modified RECIST v1.1 criteria. rPFS is defined as the time from the first study drug administration to first objective evidence of radiographic disease progression assessed by the Study Investigator, or death, whichever occurs first.

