### **3. STUDY PATIENT POPULATION AND DISCONTINUATION**

#### **3.1 Inclusion Criteria**

Patients must meet the following criteria in order to be included in the research study:

1. Written informed consent, according to local guidelines, signed and dated by the patient or by a legal guardian prior to the performance of any study-specific procedures, sampling, or analyses.
2. Males who are at least 18 years-of-age at the time of signature of the informed consent form (ICF).
3. Patients with histological, pathological, or cytological confirmed diagnosis of advanced or metastatic castration resistant adenocarcinoma of the prostate excluding neuroendocrine differentiation or small cell features who have had disease progression per Prostate Cancer Working Group 3 (PCWG3) (Scher et al. 2016) guidance following standard treatment, including approved taxane-based chemotherapy, or who are not amenable (intolerability, patient choice) to standard therapies, or for whom no therapy of proven efficacy exists.
4. Progressive disease per PCWG3 guidance documented by either:
  - Positive bone scan (at least 2 new lesions) or metastatic lesions on computed tomography (CT)/magnetic resonance imaging (MRI) (Appendix B) that can be followed for response.

Or

- If PSA criteria is the only indication of progression, then the PSA values with a starting value of  $\geq 1.0$  ng/mL that have increased on at least 2 occasions obtained a minimum of 1 week apart.

5. Patients must have progressed on at least 2 prior approved systemic therapies (in any setting), with at least 1 being abiraterone, or enzalutamide, or apalutamide or darolutamide.
6. Patients must have had surgical or ongoing medical castration. Surgical castration is defined as bilateral orchiectomy. Medical castration is defined as ongoing ADT with a gonadotropin releasing hormone (GnRH) analog or inhibitor, plus serum testosterone level <50 ng/dL (or <1.7 nmol/L).
7. Eastern Cooperative Oncology Group (ECOG) Performance Status score of 0 to 1 (Appendix A).
8. Acceptable organ functions, as evidenced by the following laboratory data:
  - Renal function, as follows:
    - Creatinine clearance of  $\geq 50$  mL/min by the Cockcroft-Gault equation or equivalent
  - Liver function, as follows:
    - Total bilirubin  $\leq 1.5 \times$  ULN (unless the patient has Grade 1 bilirubin elevation due to Gilbert's disease or a similar syndrome involving slow conjugation of bilirubin)

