### **10.3 Analysis Population**

The following analysis populations will be used:

- Full Analysis Set (FAS)/ Safety Analysis Set (SAS) is defined as all patients who have received at least one dose of study treatment. Patients will be included in the cohort in which they have been actually treated.
- Efficacy Evaluable Set (EFF) is defined as all patients who have received any dose of study treatment and have at least one adequate post-baseline response assessment.
- PK Analysis Set includes patients who were dosed with AC176 and have any sample collection of blood with measurable concentration of AC176 in plasma.

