**Table 7      Overall radiological response – RECIST v1.1 and bone progression (PCWG3)**

Overall visit soft tissue response (RECIST 1.1)	Bone progression status (PCWG3)	Overall radiological response
CR	No bone lesions at baseline	CR
CR, target lesions were present at baseline	Non-PD or NE	PR
CR, only non-target lesions present at baseline	Non-PD or NE	Non-CR/Non PD
PR	Non-PD or NE	PR
SD	Non-PD or NE	SD
No soft tissue lesions at baseline	Non-PD or NE	Non-PD
PD	Any	PD
Any	PD	PD

CR = complete response, PR = partial response, SD = stable disease, PD = progressive disease, NE = not evaluable

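### The ORR objective is limited to patients with measurable disease, but Section 10.4.2 computes ORR on the whole EFF, which includes patients who cannot score CR or PR under Table 7

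*Protocol*

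**What the plan says.** The ORR objective in Table 3, repeated in the synopsis, reads "Evaluate the preliminary anti-tumor activity of AC176 on objective response rate (ORR) for patients with measurable disease". The analysis text does not carry that restriction. Section 10.4.2 says "All efficacy analyses will be performed using the EFF" and the efficacy text of the synopsis says the same. In Section 10.4.2, ORR is "defined as the proportion of patients with confirmed complete response (CR) or partial response (PR" with confirmation at least 4 weeks apart, and measurable disease is not mentioned.

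Section 10.3 defines the EFF as "all patients who have received any dose of study treatment and have at least one adequate post-baseline response assessment". It defines no response-evaluable or measurable-disease set.

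For ORR, Section 10.4.2 adds that "patients without a post-baseline tumor assessment will be classed as not evaluable (NE) and considered as non-responders" and asks for Clopper-Pearson 95% intervals at each dose level.

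Inclusion criterion 4 in Section 3.1 accepts progression shown by "Positive bone scan (at least 2 new lesions) or metastatic lesions on computed tomography" or MRI, with a separate PSA route that begins "If PSA criteria is the only indication of progression". Neither this criterion nor any other requires a measurable lesion.

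Table 7 in Appendix B combines the soft-tissue and bone findings into one overall response. It has a row for "No soft tissue lesions at baseline", for which the best possible result is Non-PD.

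**The concern.** The objective and the analysis section give ORR two different denominators. A programmer who follows Section 10.4.2 literally produces a rate over all EFF patients, including some who cannot be classed as responders whatever the drug does. That rate then depends partly on disease pattern at entry.

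ORR is a secondary endpoint with an interval at each dose level. Section 10.2 lists preliminary anti-tumor activity among the data that inform the expansion dose, Section 5 says Part B will support the RP2D, and the exploratory biomarker objectives correlate markers with ORR. A Part A level holds at most 12 patients including backfill, and a Part B cohort about 30. At these sizes the share with measurable disease can easily differ between groups by chance, and that difference would enter the reported ORR.

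**Working it through.** The protocol states no assumed ORR, power or precision, so there is no planned figure to reproduce. The check is of consistency, followed by an illustration.

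**Step 1. Who can score CR or PR (Appendix B, response tables and Table 7)**

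| Disease at baseline | Best possible overall response | Can count as a responder? |
|---|---|---|
| At least one target (measurable) lesion, with or without bone lesions | CR or PR | Yes |
| Only non-target soft-tissue lesions, no bone lesions | CR | Yes |
| Only non-target soft-tissue lesions, plus bone lesions | Non-CR/Non-PD | No |
| No soft-tissue lesions | Non-PD | No |

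**Step 2. Can the last two groups be in the EFF?** Yes. Eligibility does not exclude them, and the EFF needs only a dose and one adequate post-baseline response assessment. The same set serves PSA response, rPFS and PFS, for which these patients are meant to count.

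**Step 3. Dilution.** Let m be the share of EFF patients with measurable disease and p their ORR. Let q be the share with only non-target soft-tissue disease and no bone lesions, and r their CR rate. Then

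EFF ORR = m × p + q × r.

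If q is negligible, EFF ORR = m × p, and it cannot exceed m.

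**Step 4. Illustration.** The documents give none of m, p, q or r. All values below are assumptions, with q = 0.

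- p = 20%: m = 40% gives 0.40 × 20% = 8%; m = 60% gives 12%; m = 80% gives 16%.
- Part B cohort of 30 with 15 measurable and 3 responders: 3/15 = 20.0% (Clopper-Pearson 95% CI 4.3-48.1%) against 3/30 = 10.0% (2.1-26.5%).
- Part A level of 12 with 6 measurable and 2 responders: 2/6 = 33.3% (4.3-77.7%) against 2/12 = 16.7% (2.1-48.4%).
- Two groups with the same p = 20% but m = 30% and m = 70%: expected EFF rates of 6% and 14%. In 12 patients these are 12 × 0.06 = 0.7 and 12 × 0.14 = 1.7 expected responders.

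**The case against.** The strongest reply is that the restriction is already in the protocol. Table 3 states it, Section 10.4.2 only names the parent set, and ORR could be taken in the measurable-disease subset of the EFF. DoR is an example: it is also an EFF analysis but by its definition covers responders only. An SAP could spell this out. The difficulty is that the definition of DoR limits it to responders, whereas the definition of ORR in Section 10.4.2 contains no such limit. The subset reading needs an exception that the section does not make. The protocol has also already fixed the ORR analysis set, definition, non-responder rule and interval method. An SAP that restricted the denominator would depart from Section 10.4.2, and one that did not would depart from Table 3.

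A reader might infer that every patient who enters on PSA or on bone scan alone dilutes the rate. The documents do not support that. Criterion 4 describes how progression was shown, not which lesions are present. A patient with stable measurable nodes and a rising PSA enters by the PSA route and can still reach PR or CR. A positive bone scan does not exclude soft-tissue disease, and Appendix B allows a lytic or mixed bone lesion to be measurable through its soft-tissue component. Nor are all patients without target lesions excluded from response, as the second row of the table shows.

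It is also fair that ORR drives no formal rule here. The primary objective is safety, no threshold or comparison of doses or AR cohorts uses ORR, and dose choice rests on all the data. Baseline disease characteristics will be tabulated. At 3 to 12 patients per level, sampling error is larger than the 6% against 14% contrast. These points limit the consequence but do not reconcile the two texts.

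**Conclusion.** The point holds. As written, Section 10.4.2 and the synopsis efficacy text give an ORR whose denominator is wider than the population in the stated objective. The patients who certainly dilute it are EFF patients with no soft-tissue lesions at baseline and those with only non-target soft-tissue lesions plus bone lesions.

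The size cannot be stated from the documents. The 8-12% against 20% is conditional on an assumed 20% ORR, an assumed m of 40-60%, and no responses outside measurable disease. A claim that ORR will be halved, or that doses will be wrongly ranked, would go beyond what the protocol shows. The defect is one of definition in a secondary endpoint, worth correcting before any response data are summarised.

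**What to change.** In Sections 10.3 and 10.4.2 and the synopsis, define the ORR denominator as treated patients with at least one measurable lesion at baseline by Appendix B. State that those without a post-baseline tumor assessment stay in this denominator as non-responders, as Section 10.4.2 already intends. This also removes a tension with the EFF, whose requirement of an adequate post-baseline response assessment may already drop some of the patients whom that rule is meant to count. Report the number with measurable disease for each dose level and each Part B cohort beside the rate. Leave the population for PSA response, TTP, rPFS and PFS unchanged.

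The cost is wording only, since baseline CT/MRI and bone scans are already required at screening. The denominator shrinks and the interval widens: in the illustration, from 2.1-26.5% to 4.3-48.1%. Patients with only non-target soft-tissue disease and no bone lesions, who could reach CR, leave the ORR analysis. That is consistent with the objective as stated, but the text should say so.

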#### 10.4.3 Safety Analysis

Safety will be assessed through the analysis of the reported incidence of treatment-emergent AEs. Treatment-emergent AEs are those with an onset on or after the initiation of therapy and will be graded according to NCI [CTCAE Version 5.0](#).

The AEs will be coded using the current version of Medical Dictionary for Regulatory Activities (MedDRA; <https://www.meddra.org/about-meddra/>) and summarized using system organ class and preferred term by dose level for all patients in the Safety Analysis Set. In addition, summaries of serious adverse events (SAEs), AEs leading to dose modification (dose hold, reduction, and discontinuation), AEs by maximum NCI CTCAE grade, and AEs related to study treatment will also be presented by dose level.

Other safety endpoints, including laboratory results, vital signs, ECG, and ECOG findings, will be summarized for all patients in the Safety Analysis Set.

Concomitant medications will be coded using the World Health Organization Drug Dictionary (WHO DD; <https://www.who-umc.org/>), and they will be listed and summarized by dose level.

*CONFIDENTIAL*

Study Drug: AC176

Sponsor/Development Innovations Study Number: AC176-001/GU 207

Final Protocol: 10 July 2023 Version 4.0

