**SOA 1 Footnotes:**

- \* Pre-screening for AR mutation status is required in the Backfill and Expansion cohorts. If patients provide historic ctDNA testing results of a positive AR point mutation, then pre-screening ctDNA testing for AR mutation status by ctDNA testing is not needed. All patients will retrospectively undergo central laboratory testing for AR mutation confirmation at Cycle 1 Day 1 per the treatment SOA (see Section 7.2).
- a A separate pre-screening informed consent form (ICF) must be signed by the patient prior to the collection of any pre-screening data or procedures.
- b A blood sample for ctDNA testing for AR mutation status is required at pre-screening for patients enrolling in Backfill and Expansion cohorts without AR point mutation documentation.
- c Written ICF for the main study must be obtained prior to initiation of study treatment and before undertaking any screening procedures.
- d During the Screening visit, review of inclusion criteria, informed consent, and medical history, concomitant therapy, and demographics, adverse events, and echocardiogram (ECHO) should take place within 28 days of start of study treatment. Tumor assessments (scans), and the PSA, and testosterone sample should be performed/collected  $\leq 28$  days prior to first dose of study drug administration.
- e The following screening parameters should be done  $\leq 14$  days prior to first dose of study drug administration: physical examination (including height and weight), Eastern Cooperative Oncology Group (ECOG) performance status, triplicate electrocardiograms (ECGs), vital signs, hematology (including absolute lymphocyte count, absolute neutrophil count, red

CONFIDENTIAL

Study Drug: AC176

Sponsor/Development Innovations Study Number: AC176-001/GU 207

Final Protocol: 10 July 2023 Version 4.0

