#### **Reporting Period for Adverse Events**

*CONFIDENTIAL*

Study Drug: AC176

Sponsor/Development Innovations Study Number: AC176-001/GU 207

Final Protocol: 10 July 2023 Version 4.0

All AEs regardless of seriousness or relationship to AC176 treatment (called study treatment), spanning from the signing of the ICF until 30 calendar days after discontinuation or completion of study treatment as defined by the study for that patient after his last dose of study drug, are to be recorded on the corresponding screen(s) included in the eCRF.

All AEs resulting in discontinuation from the study should be followed until resolution or stabilization. All new AEs occurring during this period must be reported and followed until resolution unless, in the opinion of the Investigator, the AE or laboratory abnormality/ies is/are not likely to improve because of the underlying disease. In this case, the Investigator must record his or her reasoning for this decision in the patient's medical record.

Thirty days after completion of protocol-specific treatment or discontinuation, only AEs, SAEs, or deaths assessed by the Investigator as treatment-related are to be reported.

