#### **11.3.2 Persistent or Recurrent Adverse Events**

A persistent AE is one that extends continuously, without resolution, between patient evaluation time points. Such events should be recorded only once on the SAE Report Form (if applicable) and/or the AE eCRF screen. Changes in AE grading of persistent AEs should be entered separately in the AE eCRF.

A recurrent AE is one that occurs and resolves between patient evaluation time points and subsequently recurs. All recurrent AEs should be recorded on an SAE Report Form (if applicable) and/or AE eCRF screen.

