#### **11.3.6 Pre-Existing Medical Conditions**

A pre-existing medical condition is one that is present at the start of the study. Such conditions should be recorded on the General Medical History of the eCRF screen. A pre-existing medical condition should be recorded as an AE or SAE only if the frequency, severity, or character of the condition worsens during the study. When recording such events on an SAE Report Form and/or AE eCRF screen, it is important to convey the concept that the pre-existing condition has changed by including applicable descriptors.

*CONFIDENTIAL*

Study Drug: AC176

Sponsor/Development Innovations Study Number: AC176-001/GU 207

Final Protocol: 10 July 2023 Version 4.0

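### Treatment-emergent AEs are defined by onset alone, so an AE that begins between consent and first dose and then worsens on AC176 is left out of TEAE incidence

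*Protocol*

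**What the plan says.** Section 10.4.3 makes TEAE incidence the core of the safety analysis: "Safety will be assessed through the analysis of the reported incidence of treatment-emergent AEs". It then defines the term: "Treatment-emergent AEs are those with an onset on or after the initiation of therapy". The Safety Analysis paragraph of the synopsis uses the same definition. Neither place mentions worsening or an end to the window.

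Collection starts earlier than the definition does. Section 11.1.5 has all AEs recorded, whatever their cause, over a period "spanning from the signing of the ICF until 30 calendar days after discontinuation or completion of study treatment". Beyond that period, "only AEs, SAEs, or deaths assessed by the Investigator as treatment-related are to be reported". The footnotes to SOA 1 put the screening AE review among the procedures that "should take place within 28 days of start of study treatment".

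Two recording rules deal with change over time. For a persistent AE, Section 11.3.2 says "Such events should be recorded only once on the SAE Report Form (if applicable) and/or the AE eCRF screen" and adds "Changes in AE grading of persistent AEs should be entered separately in the AE eCRF". For a condition present at the start of the study, Section 11.3.6 says it is "recorded as an AE or SAE only if the frequency, severity, or character of the condition worsens during the study".

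**The concern.** A treatment-emergent rule should separate what was there before the drug from what appeared or got worse on it. A rule that looks only at onset captures what appeared and can miss what got worse. Here the protocol collects pre-dose AEs and their grade changes, but the analysis rule has no place for a grade change.

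Safety and tolerability are the primary objective. DLTs cover only Cycle 1 of dose escalation and exclude Backfill patients. For Backfill, for the up to 60 patients in Part B and for every cycle after the first, the AE tables by dose level are the main AE summary, and Part B is meant to support the choice of the recommended Phase 2 dose. An event that was Grade 1 in screening and Grade 3 on drug is one those tables should show. Its omission makes the drug look safer than it was.

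**Working it through.** The protocol has no figure to reproduce, because the point concerns a definition. The check is to take each kind of event through the recording rules and then through the onset rule.

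1. **Condition present at study start, worsens on drug.** Section 11.3.6 makes it an AE when it worsens. The first AE record is created at that point and would naturally be dated then, although the section does not say so. Onset falls after first dose, so it is counted.
2. **AE starts after consent, resolves, and recurs on drug.** Section 11.3.2 treats a recurrence as an event to be recorded in its own right. Its onset falls after first dose, so it is counted.
3. **AE starts after consent, is still present at first dose, and rises in grade on drug.** Section 11.3.2 makes it one persistent event with a pre-dose onset. The grade change is entered separately, but no section says that this entry is a new onset. Under the definition as written, it is **not counted**.
4. **New AE from first dose to 30 days after treatment ends.** It is recorded whatever its cause, and counted.
5. **New AE after that.** It is reported only if judged treatment-related, and then counted, because the definition has no end.

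Case 3 is the defect. It can arise because the recording period opens at consent, up to 28 days before dosing. Section 11.1.5 itself expects AEs before study treatment is assigned, with biopsies and medication washout among its examples.

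How much one such event matters follows from cohort size. If n patients were treated at a dose level, one omitted patient lowers the observed incidence of that event by 1/n:

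- n = 3 (first escalation cohort): 1/3 = 33 percentage points
- n = 6 (expanded cohort): 1/6 = 17 points
- n = 12 (with Backfill): 1/12 = 8 points
- n = 30 (one Part B cohort): 1/30 = 3 points

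This is the effect of one event if it occurs. The protocol gives nothing from which to estimate how often it will.

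**The case against.** The best case for leaving the text alone has four parts.

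- **The recording rules already handle worsening.** A reader might infer from the onset rule that any baseline symptom or toxicity that worsens is lost, especially since Exclusion 2 admits Grade 1 and, with sponsor approval, some chronic Grade 2 toxicities. The protocol does not support that. Those are pre-existing conditions, and Section 11.3.6 turns their worsening into an AE. This part stands and confines the point to AEs that begin between consent and first dose.
- **The separate grade entry might rescue the event.** If its date were read as an onset, the worsened AE would count. The protocol does not say so, and recording the event once points the other way. At the least, the recording and analysis rules are not linked.
- **Other analyses would show the event.** DLTs are defined by occurrence in Cycle 1, the SRC reviews all available safety data, and laboratory, vital-sign and ECG findings are summarised separately. The further summaries in Section 10.4.3, including the one by maximum grade, do not repeat the words treatment-emergent, so it is open whether they carry the same restriction. This stands, and it rules out any inference that escalation decisions are affected. It does not restore the event to TEAE incidence, and laboratory or ECG tables do not show symptomatic events such as fatigue or nausea.
- **The end of the window belongs in the SAP.** A reader might infer that late related events will inflate the related share of AEs. That would follow only if no cut-off is set elsewhere, and a SAP commonly sets one. Taken alone, the missing end date is not a finding.

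**Conclusion.** The point holds in a narrow form. Section 10.4.3 and the synopsis fix an onset-only rule. Read with Sections 11.1.5 and 11.3.2, that rule leaves out of TEAE incidence an AE that starts between consent and first dose and then increases in grade on AC176. The protocol states this rule rather than deferring it, so a SAP that follows the protocol inherits the omission.

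The conclusion assumes that a persistent AE keeps its original onset date when its grade changes, which is the plain reading of Section 11.3.2. The direction is known: TEAE incidence can only be understated. The number of patients cannot be stated, because the protocol gives no AE rates. It is probably small, since the event must begin within at most 28 days, persist to first dose and then worsen. The correction is worth making because it concerns the primary objective and costs little; it is no reason to doubt dose escalation.

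**What to change.** In Section 10.4.3 and in the synopsis, define a TEAE as an AE whose onset, or whose increase in CTCAE grade over the pre-dose grade, falls on or after the first dose and no later than 30 days after the last dose. The 30 days match the all-cause collection period in Section 11.1.5. List treatment-related events reported after that separately.

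The cost is one sentence in two places and one added derivation comparing on-treatment grade with pre-dose grade. No new data should be needed, since Section 11.3.2 already requires grade changes to be entered; confirm that each such entry carries its date. Reported TEAE incidence may come out slightly higher.
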